10.3.2.3 Analysis of the secondary efficacy variables

The primary analysis of secondary efficacy variables will be performed in PPS, sensitivity analyses might be performed in the FAS. The secondary efficacy variables, except for the clinical outcomes, will be analyzed using similar statistical methods as for the primary efficacy variables, i.e. the MCP-Mod method with the same standardized candidate dose-response shapes (with the proper direction: increasing or decreasing trend) and corresponding coefficients as for the primary variables. In addition to analyses comparing population means in the different dose groups, the number of patients in whom the individual change from baseline value crossed clinically meaningful thresholds will be analyzed. The totality of

evidence for the primary and secondary efficacy variables will be combined and used to assess the drug effect over dose levels.

Time to clinical outcome events since randomization (using both separate and composite outcomes) will be described by means of life table statistics and Kaplan-Meier estimates.

All other efficacy variables will be analyzed descriptively.

Further details will be described in the SAP.

10.3.2.4 Analysis of the safety variables

If not indicated otherwise, evaluation of safety variables will be done using the SAF.

Adverse events

The adverse events (AE) analysis will be performed as treated in the SAF. All tabulations will be descriptive only.

Individual listings of AEs will be provided. The incidence of treatment-emergent AEs and drug-related (treatment-emergent) AEs will be tabulated by treatment group using MedDRA terms. Separate tables and listing for serious AEs and death will be provided.

Further safety parameters

The safety evaluation of laboratory data will include:

- Descriptive analysis of continuous laboratory parameters, and their changes from baseline by visit and treatment group.
- Incidence rates of treatment-emergent laboratory values outside of normal range by treatment group.
- Listings of laboratory data out of normal range.

Vital signs and their changes from baseline will be analyzed descriptively by visit and by treatment group.

ECG-findings (like AV-conduction abnormalities) will be summarized in frequency tables. A table displaying the number of patients with AV-block > I° will be provided.

Data from the AVIVO monitoring will be summarized; details will be described in the SAP.

Summary statistics and figures of heart rate and blood pressure (systolic, diastolic, and mean arterial pressure) will be created.

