5.1 Design overview

Study 15128 is a randomized, double-blind, placebo-controlled, parallel group, multicenter, Phase II study. [Figure 5–1](#) displays the overall study design.

Figure 5–1: Study design overview

Abbreviations: CV = cardiovascular; ICF = informed consent form; W = week

Approximately 384 patients from approximately 90 study centers worldwide will be randomized to one of the active treatment dose arms or placebo, in addition to standard of care heart failure therapy (for details see [Section 7](#)).

The study will comprise a 1-week run-in period, 20-week treatment period, and a 6-week follow-up period (27 weeks total).

Patients will have site visits at weeks -1, 0 (baseline), 4, 8, 12, 20 (end-of-treatment visit) and 24 (safety follow-up visit). In addition, 2 phone calls at weeks 2 and 26 will be made to assess patients' safety, and one additional phone call - to remind the patients of AVIVO self-application at Week 19.

LVEF will be measured by echocardiography at baseline and end of treatment, NT-proBNP will be measured at baseline, Week 4 and end of treatment. Safety will be monitored throughout the study. PK samples will be taken from all patients at dedicated time points. Additional biomarkers reflecting the pharmacodynamic activity of the drug will be examined, as well as candidate biomarkers that may predict drug response.

For detailed visit descriptions and rules for patients who discontinue study treatment earlier, please see [Sections 9.1](#) and [9.2](#).

The anticipated duration of the study as a whole is approximately 19 months: this includes an anticipated recruitment period of 13 months followed by a run-in period of 1 week, a treatment period of 20 weeks and a follow-up period of 6 weeks after enrollment of the last patient into the trial.

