9.2.1 Visit 1 (Week -1, run-in)

- Confirm signed informed consent is available (Section 13.4)
- Allocate unique patient identification number (Section 6.5)
- Eligibility assessment (Sections 6.1 and 6.2)
- Demographic data collection and recording (Section 9.3.1)
- Blood pressure and heart rate measurement (Section 9.6.3.4)
- Adverse events assessment (Section 9.6.1.3)
- Concomitant medication collection and recording (Section 8.1)
- AVIVO device application, worn for 7 days (Section 9.6.3.5)
- Contact card dispensing

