10.3.1.4 Safety variables

Safety and tolerability variables are:

- Adverse events (Section 9.6.1), including
 - SAEs, AEs, treatment-emergent AEs and AEs of special interest, including AV blocks > I°
 - SAEs and AEs leading to discontinuation of interruption of study drug, including AV blocks in particular
- Laboratory abnormalities (Section 9.6.3.1), measured values and change from baseline, in particular
 - Change in renal function measured by eGFR change from baseline
 - Change in liver function measured by bilirubin (total and fractions), AST and ALT from baseline
- 12-ECG abnormalities (Section 9.6.3.3) and PR interval duration
- Blood pressure and heart rate (Section 9.6.3.4); measured values and change from baseline
- Number of clinically significant findings in ECG and / or AVIVO device report

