6.3.6 AVIVO/HealthPatch monitoring

AVIVO Mobile Patient Management System is intended to continuously measure, record and periodically transmit ECG data.

Notifiable ECG-findings (like AV-conduction abnormalities) triggered by system/patients based, as well as reportable ECG finding according to AVIVO will be summarized in frequency tables by treatment group. ECG-findings according to HealthPatch will also be summarized in frequency tables by treatment group. A table displaying the number of patients with AV-block > I° according to AVIVO/HealthPatch will be provided by treatment group. All patients with significant ECG-finding will be listed. The definition of the findings that trigger a notifiable report is in Appendices 9.1.

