6.3.7 Other safety measures

The last pre-treatment safety measurement, i.e., SBP(systolic blood pressure), DBP(diastolic blood pressure), weight, body temperature, heart rate, respiration rate and electrocardiogram (12 lead ECG) will be used as “baseline value.”

When more than one value is collected at the same post-baseline visit, the value retained at that particular visit for summary statistics will be the average of the different measures reported for that visit.

For each treatment group, vital signs will be tabulated and summarized by visit for observed values and changes from baseline using descriptive statistics, as appropriate.

The incidence rates of treatment-emergent 12-lead ECG abnormalities will be tabulated by treatment group. A descriptive analysis of continuous ECG parameters and their changes from baseline by visit and treatment group will also be presented. PR interval will be summarized by visit and treatment group.

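### The SAP narrows the protocol's count of patients with AV block > I° to device recordings, so no planned table counts each affected patient once across all sources

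*Protocol*

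**What the plan says.** **Protocol.** Section 10.3.2.4 groups its outputs by type. After the adverse events paragraph, under further safety parameters, it plans frequency tables of ECG findings, AV-conduction abnormalities among them, and then states: "A table displaying the number of patients with AV-block > I° will be provided". No source is named. The next item is separate: "Data from the AVIVO monitoring will be summarized; details will be described in the SAP".

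Section 10.3.1.4 brings AV block in by two routes. One is adverse events: "SAEs, AEs, treatment-emergent AEs and AEs of special interest, including AV blocks > I"°. The other is recordings: "Number of clinically significant findings in ECG and / or AVIVO device report".

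**SAP.** Section 6.3.6, on device monitoring, has the corresponding table with a source attached: "A table displaying the number of patients with AV-block > I° according to AVIVO/HealthPatch will be provided by treatment group". Section 6.3.7 covers the standard ECG: "The incidence rates of treatment-emergent 12-lead ECG abnormalities will be tabulated by treatment group". AV block is not itemised there. Section 6.3.3 tabulates all treatment-emergent AEs by MedDRA term, those leading to permanent withdrawal or interruption, and AEs of special interest.

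The document history in SAP section 7 records that wording in 6.3.6 was altered in version 2.0. It neither describes a narrowing relative to the protocol nor gives a reason for one.

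**The concern.** Higher-degree AV block is the undesired effect that both documents single out from the mode of action (protocol section 3.4, SAP section 1). Both also say that the final choice of target dose depends partly on safety. The number of patients per dose with second- or third-degree block is therefore a figure that the dose decision will look for.

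The SAP has one table labelled as that number, and it draws on intermittent device wear only. A block first seen on a scheduled 12-lead ECG, or reported as an AE between wear periods, does not enter it. A reader who takes the label at face value would read a device-period count as the trial's patient count.

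**Working it through.** **Step 1. Device coverage.** The plan states no coverage figure, so there is none to reproduce. From the visit schedule (protocol Table 9-1 and section 9.2):

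- Treatment period: 20 × 7 = 140 days.
- AVIVO wear on treatment: 7 days from Week 0, 7 from Week 8 and 7 from Week 19, nominally days 0–7, 56–63 and 133–140. The Week -1 wear is before treatment.
- Coverage: 3 × 7 = 21 days; 21 / 140 = 15.0%.
- Against the treatment-emergent window, which runs to 6 weeks after the last dose: 140 + 42 = 182 days; 21 / 182 = 11.5%.
- Unmonitored gaps on treatment: 56 − 7 = 49 days and 133 − 63 = 70 days.

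These are nominal AVIVO figures. SAP section 6.4.3 marks HealthPatch as Japan only, and neither document gives its wear schedule.

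**Step 2. What coverage means for an episode.** Assume that onset is uniform over the 140 days, the episode lasts L days, the device is worn as scheduled, and any overlap is detected. Onset times that overlap a wear period then total 21 + min(L, 49) + min(L, 70) days.

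| L (days) | Overlapping onset days | Share of 140 |
|---|---|---|
| 0 (momentary) | 21 | 15% |
| 7 | 21 + 7 + 7 = 35 | 25% |
| 28 | 21 + 28 + 28 = 77 | 55% |
| 56 | 21 + 49 + 56 = 126 | 90% |

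The shortfall is large for intermittent block and small for long-lasting block. The documents do not say which to expect.

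**Step 3. Where a block missed by the device table appears.**

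| SAP output | What it captures | Why it is not the missing count |
|---|---|---|
| 6.3.6 device table | Blocks > I° during wear | Omits 12-lead and clinically reported blocks |
| 6.3.7 12-lead table | Treatment-emergent ECG abnormalities | AV block > I° not itemised; 12-lead only |
| 6.3.3 treatment-emergent AEs | Blocks reported as AEs | Protocol 9.6.3.3 requires a 12-lead finding to become an AE only if clinically relevant |
| 6.3.3 AEs of special interest | Third-degree blocks; Mobitz I with drug withdrawal or interruption; Mobitz II with either of these or a therapy change; from ECG or device | Second-degree blocks without these consequences fall outside |
| 6.3.3 AEs leading to withdrawal | Blocks that stop treatment | Subset of the AE table |

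**Step 4. Can the tables be combined?** No. One patient may stand in several rows, so adding them double-counts, while the largest single row is only a lower bound. The number of distinct patients per dose cannot be recovered from these summaries.

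**The case against.** The strongest reply is that nothing disappears. A reader might infer that blocks found outside device wear drop out of the analysis. The documents do not support that: they go into the 12-lead, AE, special-interest and withdrawal tables, and the special-interest table is itself patient-level, by treatment group and not tied to wear days. This part of the reply stands.

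A reader might also infer that a harmful dose will look cleaner, because a patient who develops block in, say, Week 5 and stops the drug has no later device application scheduled. Such a patient can indeed be absent from the device table. But stopping the drug for Mobitz I or II is exactly what brings the case into the special-interest rows, third-degree block enters them regardless, and the withdrawal table counts the patient again. The plan as a whole does not hide such a case, and nothing in the documents quantifies a loss that differs between doses.

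Third, the protocol never says that the table pools sources. It sits apart from the AE paragraph, protocol section 9.6.3.5 names block above first degree among the things AVIVO detects, and section 10.1 leaves further detail on outputs to the SAP. A device table is thus a possible reading. The multi-source reading is an inference, though a well-supported one, since section 10.1 cannot by itself explain why a table listed apart from AVIVO became AVIVO-only.

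Finally, pooling would not find everything. A silent, brief block between wear periods is missed by any table unless a scheduled 12-lead ECG happens to catch it, and the unscheduled visit in protocol section 9.2.11 lists no ECG.

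**Conclusion.** The point holds as a gap in safety reporting. The SAP limits the protocol's source-neutral table to device recordings, nominally 15% of treatment days for AVIVO, without recording this as a change. The blocks left out of that table are reported elsewhere, but in overlapping tables that give no de-duplicated number of patients by dose. The one table labelled as that number can understate it.

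The size depends on how long blocks last. Under the uniform-onset assumption and full detection during wear, the device table would miss 85% of momentary episodes (100 − 15), 45% of 28-day episodes (100 − 55) and 10% of 56-day episodes (100 − 90). These are shares of episodes, not predictions of patient numbers. The documents give no expected rate of AV block, so no count per arm can be derived from them. The point does not touch the primary efficacy test, and it does not show that the plan would conceal harm at any dose.

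**What to change.** In SAP sections 6.3.6 and 6.3.7, define the AV block > I° table as the number and percentage of SAF patients, by treatment group, with at least one treatment-emergent second- or third-degree AV block from any collected source: AVIVO or HealthPatch, 12-lead ECG, or AE/SAE term. Count each patient once, by highest degree. Add sub-rows by source, so that the device-only count is kept. State that run-in recordings do not count as treatment-emergent, and list which device categories in SAP appendix 9.1 and which MedDRA terms qualify.

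If the device-only table is intended, record it in SAP section 7 as a change from the protocol, give the reason, and put the wear periods in the table title.

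The cost is SAP wording and one merged table, with no new data collection. The real work is matching records of the same episode across device reports, ECG pages and AE pages. Because each patient is counted once, that matching affects the degree and source rows more than the total.

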10.3.2.5 Pharmacokinetic analyses

Pharmacokinetic analyses will be performed on the population valid for pharmacokinetics.

For the investigation of systemic exposure to BAY 84-3174 and its relationship with treatment effects, the plasma concentrations of BAY 84-3174 will be determined at different time points using a sparse sampling approach in all participating patients (see Section 9.5). The plasma concentration vs. time data will be evaluated descriptively separated by dose and visit. Plots will be prepared pooling all individual plasma concentrations (naive pooling) vs. actual relative study times (time of sample collection after time of study drug administration).

Furthermore, the pharmacokinetic data and the relationship of markers of BAY 84-3174 exposure (e.g. C_{max} , AUC) with treatment effects will be evaluated using non-linear mixed effect modeling (NONMEM). The latter evaluation will be described in a separate analysis plan and will be reported under separate cover.

The PK bioanalysis will be performed under the responsibility of the Sponsor's Bioanalytics Laboratory.

10.3.2.6 Biomarker analyses

Biomarker data will be described by the following summary statistics: arithmetic mean, standard deviation, median, quantiles, minimum, and maximum.

Graphical displays of individual data as well as mean values with standard deviation will be included.

10.3.3 Missing data, censoring due to death, and drop outs

Generally, missing data will be handled as such, i.e., no imputation of missing data will be performed. An exception is the analysis of the primary and secondary efficacy variables (except for the clinical outcomes), as described below, and the timing of events relative to other events. For this purpose, data rules for the handling of missing or incomplete dates will be described in the SAP.

All missing or partial data will be presented in the patient data listing as they are recorded in the eCRF.

A number of descriptive analyses will be performed to better understand missing data patterns. The frequency, proportion and the reasons for premature discontinuation of both the study and study treatment will be reported. Kaplan-Meier plots for "time to end of study treatment (calculated as days from first dose to the earliest date of last dose, including premature stop of study medication and death)" and "time to end of study" will be provided, by treatment group and overall.

The number of patients who prematurely discontinue study participation or intake of study medication will be carefully evaluated with respect to the key baseline characteristics, which will be further specified in the SAP, and the reasons for premature discontinuation of study and / or study treatment. If the proportion of patients who withdraw across the dose groups is not fairly balanced, the impact on the primary variables will be further explored. To further explore the missingness pattern with regards to the "missing at random" assumption, the mean of the baseline values of the efficacy variable will be summarized for patients with and without post-baseline observations, by treatment group and overall.

For the analysis of the primary and secondary variables, it cannot necessarily be assumed that data are missing at random. As the choice of primary analysis will be based on assumptions that cannot be verified, the robustness of the results of the primary analysis will be investigated through appropriate sensitivity analyses making different assumptions, in accordance with the European Medicines Agency (EMA) "Guideline on missing data in confirmatory clinical trials".

Efficacy analysis using the PPS

The primary efficacy analysis aims at evaluating the dose-response relationship of the primary and secondary efficacy variables (except for clinical outcomes) for all randomized patients who have remained in the study and adhered to study treatment according to the study protocol until Week 20 (“completers and treatment adherers” analysis). Therefore, the primary analysis will be performed in the per-protocol set, a subset of the FAS comprising “compliant and adherent” patients (as much as possible, defined via validity criteria). To avoid bias, the PPS will also include those “compliant and adherent” patients who are “censored” due to CV death or a hospitalization for HF preventing the assessment of the relevant efficacy endpoints 20 weeks after randomization to take place as planned. It is expected that these are the only patients for whom missing observations need to be considered in the primary analysis. A “worst case” approach will be used, where the missing change from baseline value will be imputed with a multiple of the worst change from baseline value, which is possible given the individual baseline value observed in the respective treatment group, or 0 if the worst change in that treatment group is positive for LVEF / negative for NT-proBNP.

As a sensitivity analysis, a “completers and treatment adherers” only analysis excluding the censored patients in the per-protocol analysis set will be performed. This strategy leads to unbiased estimates only if missing values are “missing completely at random” (MCAR), i.e. the missingness – including missing data due to death – is independent of both observed and unobserved outcomes. This condition is unlikely to hold exactly but rather approximately.

Further sensitivity analyses on the PPS may be performed if the missing data patterns suggest further exploration.

Efficacy analysis using the FAS

The efficacy analysis in the FAS aims at evaluating the dose-response relationship of the primary and secondary efficacy variables for all randomized patients. Efficacy analyses in the FAS will include the following:

- Generally, it will be assumed that missing observations for the respective efficacy variables are missing at random. This implies that the behavior of the post dropout observations can be predicted from the observed variables using appropriate imputation models. Likely exceptions to the missing at random assumption are observations which are missing due to a patient’s CV death or HF hospitalization prior to the visit in Week 20. These observations can be assumed to be missing not at random (MNAR), i.e., that missingness depends both on observed and unobserved outcomes and that an explicit model for the patient’s statistical behavior after drop-out (or death) is required. Therefore, an analysis based on a pattern mixture framework (47) with different imputation rules depending on the reason for missingness will be used using a multiple imputation model, followed by a modification of the imputed data applying penalties:
 1. First, multiple imputation will be applied to draw sets of completed data, using an appropriate imputation model. Baseline characteristics which should be considered in the imputation model include but are not restricted to the baseline values of the respective efficacy variable, the treatment group, and sex.

2. The imputed data will be modified by applying penalties. The choice of the penalty may be guided by the worst observed change from baseline for the respective outcome in the corresponding treatment group, e.g. by choosing the penalty as a multiple of the worst observed change from baseline value.
 3. After modifying the completed data sets, the primary analysis using the MCP-step of the MCP-Mod methodology will be applied to the multiply imputed datasets and the results will be combined.
- An analysis where for each patient without an observation at the visit in Week 20 the missing value will be imputed according to a last observation carried forward approach, including the baseline value. Such an analysis is usually biased but will make use of the observations obtained at early EOT visits.

For reproducibility, the SAS seed number for creating the random numbers for the multiple imputation will be set to the study number. More details will be described in the SAP.

10.4 Determination of sample size

In the first step, this combined proof-of-concept and Phase IIb dose-finding study has been powered for the detection of a dose response signal in the primary efficacy variable change in LVEF.

The sample size for the primary efficacy variable change in LVEF was evaluated under the assumptions described in Section 10.3.2.2 and a type I error level = 5% with the aim to achieve at least 80% power for the one-sided primary multiple contrast test. The overall randomization ratio was assumed to be 3:1:2:2:2:2 for doses 0, 5, 10, 20, 30, and 40 mg.

Table 10–2 displays the power for the multiple contrast test in the MCP-Mod approach, used as primary analysis, for the set of specified alternatives.

Table 10–2: Power for multiple contrast test for set of different alternatives

Sample size		Power for alternative based on respective dose-response model (in %)					
Overall	Per group ^a	Linear	Sigmoidal E _{max} 1	Sigmoidal E _{max} 2	E _{max}	Quadratic	Minimum
240	40	73.36	86.24	81.20	82.26	79.97	73.36
252	42	75.26	87.73	82.94	83.94	81.70	75.26
264	44	77.10	89.13	84.58	85.58	83.31	77.10
276	46	78.71	90.30	85.97	86.94	84.70	78.71
288	48	80.31	91.39	87.30	88.25	86.09	80.31
300	50	81.62	92.27	88.42	89.32	87.24	81.62
312	52	82.99	93.15	89.53	90.38	88.39	82.99
324	54	84.25	93.92	90.54	91.37	89.50	84.25
336	56	85.43	94.60	91.45	92.22	90.39	85.43
348	58	86.56	95.22	92.31	93.02	91.28	86.56

^a Number of patients randomized to dose levels 10 mg, 20 mg, 30 mg, and 40 mg of neladenoson bialanate, for placebo sample size per group to be multiplied by 3/2, for dose level 5 mg sample size per group to be divided by 2.

To achieve at least 80% power for the multiple contrast test in the MCP-Mod approach under all different alternatives, a minimum of 48 patients per treatment group (72 patients for the placebo and 24 patients for the 5 mg group) is needed, resulting in an overall sample size of N = 288 patients.

In the second step, the power for the multiple contrast test in the MCP-Mod approach for the absolute change in log-transformed NT-proBNP was estimated, based on the assumptions outlined in Section 10.3.2.2 and a given sample size of $N = 288$. Statistical simulations were used to assess the power of the Hochberg test to reject at least one of the two null hypotheses. It was concluded that an overall sample size of $N = 288$ patients is sufficient to reject at least one of the two primary efficacy hypotheses with a power of about 83%.

This power would drop to less than 80%, if the relative reduction of NT-proBNP from baseline within the investigated dose range for neladenoson bialanate is $< 27.5\%$ compared to an expected reduction from baseline of 10% under placebo.

Based on these considerations, a total of 384 patients are planned to be randomized to the 6 treatment groups:

- 96 patients are planned to be randomized to placebo (0 mg),
- 64 patients each are planned to be randomized to the dose levels 10 mg, 20 mg, 30 mg, and 40 mg of neladenoson bialanate, and
- 32 patients are planned to be randomized to the dose level 5 mg of neladenoson bialanate.

These numbers already include adequate assumptions on expected drop-out after randomization and invalid or missing data. In the selected population it is expected that only about 75% of all randomized patients, i.e. about 288 patients, will contribute complete data to the primary analysis in the PPS.

All power estimations and simulations were performed with the DoseFinding package in R, version 3.0.2 (2013-09-25).

